## 1. STUDY SUMMARY

Study Title	Role of Transcranial Direct Current Stimulation to Decrease Impulsivity and Compulsivity in Individuals with Obesity
Study Design	Double-blind, randomized, sham-controlled pilot clinical study
Primary Objective	
Primary Objective: To determine if there is a treatment-related decrease in measures of impulsivity and compulsivity with tDCS compared to sham
 
Hypothesis: tDCS treatment decreases impulsivity and compulsivity.

Secondary Objective(s)	
Secondary Objectives: (1) To compare tDCS treatment-related change in weight loss compared to sham (randomized intervention) in individuals prior to undergoing their 16 week structured behavior modification weight loss program (usual care) in the Minneapolis VAMC's Move Mass Program
 
Hypothesis: tDCS treatment leads to weight loss
 
(2) To examine the history of brain injury (no TBI, single TBI, multiple TBI) in individuals with obesity as a possible factor in impulsive and compulsive eating.
 
Hypothesis: TBI as a co-morbid condition may have some impact on eating behaviors.

Research Intervention(s)/Investigational Agents	tDCS (Starstim Noninvasive Wireless neurostimulator)
IND/IDE # (if applicable)	Class IIa device
Study Population	500 Veterans will be screened to enroll up to 50 Veterans. Subjects will be recruited from Minneapolis VAMC's Move Mass Behavior Modification Classes
Sample Size (number of participants)	20 (10 will undergo tDCS and 10 will undergo sham procedure). All will undergo Brain HQ task training to enhance executive function.
Study Duration for Individual Participants	About 3-4 months

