**Research plan and methods.** We plan to enroll up to 50 individuals and complete studies in 20 individuals involved with the Minneapolis VAMC's Move Mass weight management clinic. Participants, who report that they tend to have out-of-control eating at least once per week, will be randomized to either active or sham tDCS, two 13-minute sessions separated by 20 minutes, for five consecutive treatment days; both groups will undergo brain training tasks during the treatments. After they complete the sessions subjects will complete a 16-week long structured Move Mass Behavior Modification program (usual care). In addition to the brain training tasks during the stimulation periods, subjects will complete a food-impulsivity related questionnaire (the Binge Eating Scale [BES]) and other instruments at several timepoints during the study. The effect of the active vs. sham treatment to reduce measures of impulsivity and improve measures of executive function will be assessed over time. As a secondary aim we will evaluate treatment effect on weight loss and examine the possible relationship to TBI.

**Clinical relevance.** Refractory obesity, like other conditions with an addictive component, is in part related to impulsivity and inability to change compulsive behavior. More effective treatments are needed for this condition which significantly impacts morbidity and mortality in Veterans and non-Veterans. Safer, more effective treatments, including non-pharmacologic treatments which make use of the brain's own neuroplasticity to enhance function and heal or strengthen regions involved in impulse control represents an exciting new therapy for impulse control in individuals with obesity.

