**Preliminary data.** Prior work by members of our group demonstrates that the application of tDCS does appear to improve impulse control when applied with tasks which engage regions of the brain involved in executive function. [name] and colleagues conducted a VA-based study in 30 individuals who underwent two 25-minute sessions (active tDCS vs. sham procedure coupled with performance of the Balloon Analogue Risk Task [BART]) for five days followed by sessions at one and two months. Subjects completed questionnaires and behavioral tasks measuring impulsivity (the Risk Task) before and after the intervention. After receiving active tDCS, subjects showed a significant 46% decrease in risky choice in the Risk Task from pre- to post-intervention, which persisted through the one and two-month follow-up sessions. The sham tDCS group showed no significant change in risky choice from pre- to post-intervention.

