#### **4. Study Endpoints**

**Primary Endpoint:** decrease in impulsivity and compulsion (as measured by change in NIH Examiner Score) with active tDCS compared to sham

**Secondary Endpoint:** change in weight over the study period

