### **Statistical Plan and Power Analysis**

For this pilot study our statistical approach will be similar to prior work done by members of our team, a randomized controlled design with participants randomized to either active or sham tDCS.

Power Analysis. For Aim 1, the primary comparison will be difference in change before and after training on untrained impulsivity-related tests of executive functioning between active and sham tDCS. [name] and colleagues' preliminary data found an effect size of  $d=.97$  between active and sham tDCS groups. Based on these results, the current pilot project is powered to detect an effect size of .97 with 80% power and an alpha = .05 (N = 20). Power to detect a medium effect size will be approximately .60. Thus, this study is well-powered to detect changes on the primary cognitive outcome variables.

For the secondary aim of weight loss, an ANOVA will be used with weight as the dependent variable and the grouping variable will be active vs. sham. We will be testing for a Group x Time interaction for weight.

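### The planning effect d = .97 is carried to the NIH Examiner without justification, and even if it is accepted, 10 per arm gives about 54% power, not 80%

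*Combined protocol and SAP*

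**What the plan says.** The Statistical Plan and Power Analysis (section 6) makes the primary comparison the between-arm difference in pre-to-post change on untrained executive-function tests. It cites d = .97 from a team member's preliminary data and states: "Based on these results, the current pilot project is powered to detect an effect size of .97 with 80% power", at alpha = .05 with N = 20. It adds: "Power to detect a medium effect size will be approximately .60". It concludes that the study is well-powered for the primary cognitive outcome variables.

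The sample is given in the Study Summary as "20 (10 will undergo tDCS and 10 will undergo sham procedure"). The Abstract makes clear that 20 is a number of completers: "enroll up to 50 individuals and complete studies in 20 individuals".

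The Preliminary data paragraph in section 4 describes one tDCS study, of 30 people, with "two 25-minute sessions (active tDCS vs. sham procedure coupled with performance of the Balloon Analogue Risk Task [BART"]) over five days. Participants completed "questionnaires and behavioral tasks measuring impulsivity (the Risk Task) before and after the intervention". The reported result is a 46% fall in risky choice in the active arm and no significant change under sham. No standardised effect and no SD are given.

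Study Endpoints defines this trial's primary endpoint as a decrease in impulsivity and compulsion, "as measured by change in NIH Examiner Score". The concurrent training is Brain HQ.

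**The concern.** There are two problems, and mending one leaves the other.

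The first is the input. The only described source for .97 concerns another outcome and another concurrent task. The documents report no tDCS effect on the NIH Examiner. They support that battery only as a set of executive-function tests that predicted weight loss in a cited study, and they do not argue that an effect on risky choice should carry over.

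The second is the arithmetic. The stated 80% and .60 do not follow from d, alpha and N as written. They also do not fit each other.

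What is at stake is how the result is read. Section 14 says the findings will inform larger studies. If the plan calls itself well-powered, a non-significant Examiner result could be taken as evidence that tDCS does little, when the design reliably detects only very large effects.

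**Working it through.** **Inputs.** d = .97, alpha = .05, N = 20 and about .60 for a medium effect come from the Statistical Plan and Power Analysis. The 10:10 split comes from the Study Summary. Two things are assumed because the plan does not state them: sidedness (both tried) and medium meaning d = .5. The model is a two-sample t-test on one change score, which is the comparison the power paragraph describes.

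**1. The plan's own 80%.** The noncentrality is d × √(n/2) = .97 × √5 = 2.169, with 18 degrees of freedom.
- Two-sided, critical t = 2.101: power 53.7%. The normal approximation gives Φ(2.169 − 1.960) = 58.3%.
- One-sided, critical t = 1.734: power 67.1% (normal approximation 70.0%).

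Neither reproduces 80%.

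**2. The plan's .60.** The noncentrality is .5 × √5 = 1.118. Power is 18.5% two-sided and 28.5% one-sided.

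**3. Other readings tried.** Power at d = .97 and at d = .5, two-sided unless it is an F test:

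| Reading | d = .97 | d = .5 |
|---|---|---|
| 20 per arm | 84.8% | 33.8% |
| Baseline-adjusted (ANCOVA), r = .7 | 81.9% | 31.7% |
| Repeated-measures F, 2 times, r = 0 | 82.6% | 32.2% |
| Repeated-measures F, 2 times, r = .5 | 98.4% | 56.2% |

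Some come near one of the stated figures, but only with inputs the plan does not give. None gives both.

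**4. Why the two figures conflict.** By the normal approximation, 80% power at .97 two-sided needs a noncentrality of 1.960 + 0.842 = 2.802. At d = .5 this scales to 2.802 × .5/.97 = 1.444, so power is Φ(1.444 − 1.960) = about 30%. The one-sided version gives about 36%. With 80% at .97, a power of .60 would need a medium effect of about (1.960 + 0.253)/2.802 × .97 = .77.

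**5. What the design can detect.** With 10 per arm, 80% power requires d = 1.32 two-sided (1.16 one-sided). The expected 95% CI half-width for the arm difference is 2.101 × √(2/10) = 0.94 SD of change.

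**6. What N would be needed at .97.** For 80% two-sided power, 18 per arm, or 36 completers (one-sided 14 per arm, or 28). This still takes .97 as the Examiner effect. If the true effect were .5, 18 per arm would have 31% power.

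**7. Precision of .97.** If it was observed in the 30-person study with a 15:15 split (assumed), its 95% CI is 0.20 to 1.72; with 10:20 it is 0.16 to 1.76. Using the 15:15 limits, two-sided power with 10 per arm runs from 7% to 95%.

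**The case against.** The strongest reply is that this is a pilot and that borrowing an effect from related work is normal. The two studies share a good deal: VA setting, sham control, two sessions or stimulation periods over five days, and an outcome measured before and after rather than used as the concurrent task. That makes .97 a reasonable hypothesis. It does not make the study well-powered for an outcome on which no effect has been estimated.

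The source of .97 is also not certain. The power paragraph names no outcome and the Preliminary data paragraph gives no d. The Risk Task is the only candidate described, so the link is likely but inferred. If .97 came from elsewhere, the source is undocumented and the same remedy applies.

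The planned analysis is growth curve modelling across four Examiner domains, not a t-test, and baseline adjustment or repeated measures can raise power. That stands, but the plan states no correlation or model for its power figures, and no reading tried gives 80% and .60 together. Enrolment of up to 50 does not rescue the claim either, since the power statement is for N = 20 completers. Even 25 per arm would give 92% at .97 and 41% at .5.

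Three stronger readings are tempting and should be resisted.
- A reader might infer that the power claim has no basis at any sample size. Power is conditional on an assumed effect and can be calculated: 36 completers would give 80% at .97.
- A reader might infer that Brain HQ in both arms must shrink the arm difference relative to the earlier study. The earlier sham arm also had a concurrent task, and section 4 argues that broader training may help generalisation, so the direction is unknown.
- A reader might compare total stimulation minutes. The documents do not say how much of each 25-minute session was stimulation, and they do not show that fewer minutes mean a smaller effect.

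**Conclusion.** The concern holds in two parts. The documents give no justification for applying d = .97 to the NIH Examiner; that its source is the Risk Task is a strong inference, not a stated fact. Independently, the stated power is wrong as written: about 54% two-sided (67% one-sided) at .97 instead of 80%, and about 18.5% (28.5% one-sided) at d = .5 instead of .60. The well-powered conclusion is therefore unsupported.

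These figures assume 10 completers per arm, alpha .05, a t-test on a single change score with no multiplicity adjustment, and medium meaning d = .5. A different analysis would shift them, but the inconsistency between the two stated powers remains wherever noncentrality scales with d. The documents do not say that a null result would be read as evidence against tDCS; that is a foreseeable risk of the wording, not something the plan announces.

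**What to change.** In the Statistical Plan and Power Analysis:

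1. Name the outcome, concurrent task and regimen behind d = .97, and state that no NIH Examiner estimate for tDCS is available.
2. Replace both power statements and delete the claim that the study is well-powered. Suggested content: for a two-sided .05 two-sample t-test on one change score with 10 per arm, power is about 54% at d = .97 and 18.5% at d = .5; the effect detectable with 80% power is about 1.32 SD of change (1.16 one-sided); the expected 95% CI half-width is about 0.94 SD. State the test and its sidedness beside the figures.
3. State that a non-significant Examiner result will be reported with its confidence interval and treated as inconclusive when that interval does not exclude effects of interest.

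This costs a paragraph of text, with no added participants, visits or data. The downside is that the stated sensitivity becomes less favourable.

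### The stated power is wrong: with 10 per arm it is about 54% at d = .97 (not 80%) and about 19% at a medium effect (not 60%), so the trial is not well powered

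*Combined protocol and SAP*

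**What the plan says.** The power paragraph in Section 6 (Statistical Plan and Power Analysis) defines the primary comparison for Aim 1 as the difference between active and sham tDCS in change, from before to after training, on the untrained executive-function tests. It takes a between-group effect of d = .97 from the team's preliminary data and states that the project is "powered to detect an effect size of .97 with 80% power and an alpha = .05 (N = 20"). It adds: "Power to detect a medium effect size will be approximately .60". It concludes: "Thus, this study is well-powered to detect changes on the primary cognitive outcome variables".

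The Study Summary gives the sample size as "20 (10 will undergo tDCS and 10 will undergo sham procedure"). Under Study Procedures, these 20 are the people expected to complete the study, out of 50 to be consented.

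The only preliminary tDCS study described is in Section 4 (Background, Significance, and Preliminary Data): "a VA-based study in 30 individuals who underwent two 25-minute sessions", with the Balloon Analogue Risk Task (BART) as the paired task and the Risk Task as the behavioural outcome.

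The plan does not state whether the test is one- or two-sided, which SD standardises d, any pre-post correlation, or what d counts as medium.

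**The concern.** Ten per arm is a small sample for a between-group effect just under one SD, and 80% power looked too high on sight. The second figure looked worse: 60% power at a medium effect with 20 people in total is far from what a two-arm comparison can deliver. The two figures also sit too close together, because power falls steeply when the effect is roughly halved.

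These figures are the whole justification for the sample size and the only basis for the well-powered conclusion. Section 14 says the results will inform larger studies. A reader who believes the trial had 80% power would take a null result as fairly strong evidence against tDCS, when the design would miss its own planning effect almost half the time and a medium effect about four times in five.

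**Working it through.** **Inputs**

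- d = .97 between arms; alpha = .05; N = 20; stated power 80% at .97 and about .60 at medium (Statistical Plan and Power Analysis).
- n = 10 per arm (Study Summary).
- Assumed, because the plan is silent: two-sided test; d in units of the SD of the change score; medium = .50. Alternatives are shown below.

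**Attempt to reproduce the plan's figures**

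For a two-sample t-test with n per arm, df = 2n − 2 and the noncentrality is δ = d × √(n/2). Power is the probability that a noncentral t variable with that δ falls beyond the critical value. With n = 10, df = 18, √(10/2) = 2.236 and the critical value is 2.101.

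- d = .97: δ = .97 × 2.236 = 2.169, power **53.7%** (stated 80%).
- d = .50: δ = .50 × 2.236 = 1.118, power **18.5%** (stated about 60%).

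Neither figure is reproduced. Other readings of medium, with 10 per arm and a two-sided test, give 9.7% at d = .3, 24.6% at .6 and 39.5% at .8.

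**What the stated power would need**

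- 80% at d = .97: 18 per arm (80.7%); 17 per arm gives 78.3%.
- 60% at d = .50: 41 per arm.
- With 10 per arm, 80% power requires δ = 2.963, so d = 2.963 / 2.236 = **1.32**. Even 60% power requires d = 1.05, above the planning effect.
- 95% CI half-width for the arm difference: 2.101 × √(2/10) = 2.101 × 0.447 = **0.94 SD**.

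**Other designs and readings**

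| Reading | Power at .97 | Power at .50 |
|---|---|---|
| Stated in the plan | 80% | about 60% |
| 10 per arm, two-sided | 53.7% | 18.5% |
| 10 per arm, one-sided | 67.1% | 28.5% |
| 20 per arm, two-sided | 84.8% | 33.8% |
| 20 per arm, one-sided | 91.4% | 46.3% |
| 25 per arm, two-sided | 91.9% | 41.0% |
| Paired or one-sample, n = 20, two-sided | 98.4% | 56.5% |
| Group × Time formula, 2 visits, r = 0 | 82.6% | 32.2% |
| Group × Time formula, 2 visits, r = .5 | 98.4% | 56.2% |
| Group × Time formula, 2 visits, r = .55 | 99.1% | 60.7% |
| ANCOVA, d on raw-score SD, r = .68 | 79.6% | 30.2% |

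No row gives both stated figures.

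**The two figures against each other**

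For a given design and test, δ is proportional to d, whatever the sample size, SD scale or correlation. At df = 18:

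- 80% power at .97 means δ = 2.963. At .50, δ = 2.963 × .50/.97 = 1.527, which is 30.4% power.
- 60% power at .50 means δ = 2.339. At .97, δ = 2.339 × .97/.50 = 4.538, which is 99.0% power.

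The results are practically the same at df = 38 and df = 1000. The stated pair would agree only if medium meant d of about .77.

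**The case against.** The strongest defence is that .97 may be standardised by the raw-score SD, not the change-score SD. Baseline information then adds power: a pre-post correlation of about .68 with ANCOVA, or about .73 with change scores, brings power at .97 to about 80% with 10 per arm. On that reading the 80% is unsupported by the stated inputs rather than impossible. That much stands. But the plan gives no correlation, at r = .5 the change-score analysis is back to 53.7%, and power at .50 is about 30% even when the 80% is recovered.

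Medium is undefined, so d = .50 is an assumption. With 80% at .97, power is 41% at d = .6 and 53% at d = .7. Only about .77 would reconcile the pair, and that would still leave the 80% unsupported.

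Up to 50 may be enrolled, and people who drop out after Visit 6 could still contribute to the primary comparison, so the number analysed could exceed 20. The power sentence itself uses N = 20, however, and even 25 per arm gives only 41.0% at .50.

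The planned analysis is growth curve modelling of four NIH Examiner domains, not one t-test, so 54% is not exactly the power of that analysis either. This does not help the claim: the plan gives no power calculation for that model, and splitting alpha over four domains would cut t-test power at .97 to about 30%.

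Two milder points also stand. That .97 came from the 30-person study is an inference, though a likely one, since no other preliminary tDCS study is described. And a pilot may properly be small; the fault is in claiming power it does not have.

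**Conclusion.** The concern holds. From the plan's own inputs, power is about 54% where 80% is stated, and about 19% where 60% is stated. The well-powered conclusion has no basis.

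The exact values rest on a two-sided test, d on the change-score SD scale and medium = .50. The conclusion does not: one-sided testing gives 67% and 28%, and baseline adjustment can recover the first figure only with an unstated correlation and never the second alongside it. The inconsistency between the two figures does not depend on sample size, SD scale or correlation; it requires only that medium be well below .77.

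The planning effect adds a further doubt. It appears to come from 25-minute sessions paired with BART and assessed on the Risk Task, whereas this trial uses 13-minute stimulation periods, Brain HQ and the NIH Examiner. The power error stands without this point.

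This must be corrected, because it is a wrong figure in the sample-size justification.

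**What to change.** Replace the three power sentences in the Statistical Plan and Power Analysis with text to this effect:

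> With 10 participants per arm, a two-sample comparison of change scores at two-sided alpha .05 has about 54% power for d = .97 and about 19% for d = .50, with d in units of the SD of the change score. The effect detectable with 80% power is d = 1.32. This is a pilot study. The active-minus-sham difference will be reported with its 95% confidence interval, whose expected half-width is about 0.94 of that SD. The value .97 appears to come from preliminary work with a different outcome, paired task and session length.

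Delete the statement that the study is well powered. The sponsor should confirm the source of .97 and the SD it was standardised by. If the sponsor intended a baseline-adjusted analysis, the text should name it, give the assumed pre-post correlation and its source, and recompute both power figures under that one model.

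The cost is protocol wording only: no extra participants and no change to procedures. The stated power becomes less favourable. Keeping 80% power at d = .97 under the two-sided comparison would instead need 18 per arm, 36 in total.

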## 6. Study Methods, Procedures, and Statistical Plan

### Study Design:

For this single-site pilot study our statistical approach will be similar to prior work done by members of our team previously, a double-blind, randomized controlled design with participants randomized to either active or sham tDCS. For this study Veterans will be referred as potential candidates because they have obesity and self-report that they tend to have at least one occasion of out-of-control eating per week on average. Participants will be trained on the Brain HQ, an interactive computer software package in which subjects work through a series of structured exercises designed to stimulate neuroplasticity. Participants will be randomly assigned to receive either active tDCS or sham stimulation with their training during one hour session each day( 13 minutes of stimulation , 20 minute stimulation break, followed by 13 more minutes of stimulation) over five days. A 2 mA current will be applied with two 25 cm^2 saline soaked electrode sponges with anode at F4 (right) and cathode at F3 (left) concurrent with the Brain HQ. To evaluate generalization, an untrained NIH Examiner Battery sub-set testing 4 modalities of executive function will be performed before and after the five days of training. Subjects will then go through the Move Mass Behavior Modification after completing the five days of treatment. (This 16-week structured behavior modification program of bi-weekly sessions is usual care for these participants.) Participants will return for the trained and untrained testing at V7 (halfway through the behavior modification course) and V8 (final study visit to occur after the behavior modification course) follow-up sessions without stimulation. For the trained Brain HQ tasks, growth curve analysis (GCA) examining individual variation of the

growth rates over time will be done (across the 5 days of tDCS sessions and the subsequent follow-ups) to examine for change in individual and group trajectories over time. For the untrained NIH Examiner tasks, GCA will be used to evaluate for individual and group effects in executive function in the four domains of the NIH Examiner Battery from pre- to post-treatment and through follow-up sessions. We will also compare pre- and post- treatment results in the cravings and binging questionnaires within and between groups.

Figure 1: Study Visit Schedule

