### **Study Procedures:**

Five hundred individuals will be screened with the goal of consenting 50 patients and 20 patients completing the study. The study consists of 8 study visits including 4 testing days, one before (V2) and one on the day of the fifth session of tDCS (V6) followed by the structured 16-week long behavior modification class, and test visit half way through the 16-week class (V7) (2 months into the behavior modification class), and a final test visit 2 months later (+/- 2 weeks) (V8). At consent/screening visit (V1), baseline serum biochemistries, a general physical (including weight measurement) pregnancy test, impulsivity questionnaire (Binge Eating Scale [BES], depression screening (PHQ-9 [<https://patient.info/doctor/patient-health-questionnaire-phq-9>]), Minnesota Blast Exposure Screening Tool (MN-BEST), and executive function-related testing (NIH Examiner and Brain HQ) will be performed; these can be completed at V2 if those were not completed after consent on V1. These tests; other than the pregnancy, biochemistries, and PHQ-9; are repeated at V6-V8. While subjects are undergoing the 5 days of tDCS treatments (V2-V6) they will undergo Brain HQ testing during the treatment sessions. PHQ-9 is repeated at the final visit.

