## **11. Withdrawal of Participants**

- a. Withdrawal Circumstances: Subjects are free to withdraw from the study at any time and they may be withdrawn by the study investigators if it is deemed that it would not be safe for them to continue with the study or if subjects are not following the study-related procedures which would compromise the scientific integrity of the study.

b. Withdrawal and Termination Procedures: If a subject wishes to withdraw or is asked to withdraw from the study the participant would be asked to participate in an early end-of-study visit (procedures to be followed would be those of V8) and the subject would be asked about continued data collection of clinical data (vitals and medications) to finish out the period of time they would have participated in the study. All data collected up to the period of withdrawal or termination and as arranged with the subject through partial withdrawal would continue to be used as per study-related purposes.

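### The weight ANOVA names no visits, no rule for missing weights and no end-of-study estimate; a mixed model with a V8 contrast would be a cheap improvement (minor)

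*Combined protocol and SAP*

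**What the plan says.** - **Endpoint.** Study Endpoints gives the secondary endpoint as "change in weight over the study period" and names no visit.
- **Analysis.** Section 6, Statistical Plan and Power Analysis, specifies an ANOVA on weight by arm: "We will be testing for a Group x Time interaction for weight". It gives no levels of Time, analysis set, missing-weight rule, contrast or confidence interval.
- **Schedule.** Table 1 has weight at V1, V6, V7 and V8. Study Design describes the last of these as "V8 (final study visit to occur after the behavior modification course", and Study Procedures allows it two weeks either side.
- **Scope.** Section 14 says weight response will be evaluated both while the programme runs and once it is over, and that the arms will be compared. It adds no visit or estimate. Growth curve analysis is planned there for the cognitive tasks only.
- **Numbers.** Section 1 gives the sample size as 20, ten per arm. The Abstract says "We plan to enroll up to 50 individuals and complete studies in 20 individuals", and Study Procedures speaks of "consenting 50 patients and 20 patients completing the study".
- **Withdrawals.** Section 11 says of a withdrawing subject that "the participant would be asked to participate in an early end-of-study visit (procedures to be followed would be those of V8"; those procedures include a weight. It also seeks "continued data collection of clinical data (vitals and medications) to finish out the period of time they would have participated in the study", and provides for continued use of "All data collected up to the period of withdrawal or termination".

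**The concern.** The data-collection plan and the analysis plan do not fit together well. Section 11 takes trouble to obtain and keep weights from people who leave, but a classical repeated-measures ANOVA uses only people with every weight in the Time factor. No text says to which visit, if any, an early weight belongs. If leaving is related to weight response, the arm difference among complete records can be too large or too small, depending on who leaves and from which arm.

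Separately, an interaction test over several visits asks whether the arms' weight profiles differ anywhere. The endpoint needs one number: the active-minus-sham difference in change over the study, with its uncertainty. Section 14 says the results will inform larger studies, and this estimate is a natural input to them.

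**Working it through.** **No figure to reproduce.** The documents give no effect, SD, dropout rate or power for weight. The only power statement concerns the cognitive outcome and plays no part here.

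**Step 1: what the test is.** Interaction df = (arms - 1) x (visits - 1).
- All four weights: (2 - 1)(4 - 1) = 3 df, an omnibus test.
- V1 and V8 only: (2 - 1)(2 - 1) = 1 df. The interaction F is then the square of the t statistic comparing mean change between arms (a simulated trial gave F = 0.0762 by both routes), so the required estimate is available directly.

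**Step 2: what the omnibus test can show.** Assume 10 per arm, a real difference at V7 of 0.5 to 1 SD and none at V8. With a Greenhouse-Geisser correction, the omnibus test is significant in 13.5% to 84.5% of simulated trials; the test of V8 change is significant in 4.6% to 5.4%. The omnibus result is not a false positive, because the arms do differ at V7. It simply does not isolate V8.

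**Step 3: how many records are complete.** If each of the three post-baseline weights is missing independently with probability p (assumed), the expected number of 20 with all four is 20(1 - p)^3:
- p = 5%: 20 x 0.857 = 17.1
- p = 10%: 20 x 0.729 = 14.6
- p = 15%: 20 x 0.614 = 12.3

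**Step 4: how large the bias could be.** All inputs are assumed: weights at weeks 0, 1, 9 and 17; true V8 difference -3 kg; SD of true 17-week change s = 3 to 7 kg; measurement noise SD e = 0.5 to 1.5 kg; 24 randomised and about 20 completing (4/24 = 17% leaving). Half the leavers go at random and half because they had lost less by V7.

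| Outcome-related leaving | Complete records | Mixed model |
|---|---|---|
| Both arms, or sham only | -2.09 to -2.91 kg | -2.82 to -3.14 kg (all patterns) |
| Active only | -3.30 to -3.66 kg | as above |

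Bias in complete records therefore runs from 3 - 2.91 = 0.09 kg to 3 - 2.09 = 0.91 kg towards zero, or from 0.30 to 0.66 kg away from it.

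For scale, the half-width of the 95% CI for a difference in mean change with 10 per arm is t(0.975, 18) x sqrt(s^2 + 2e^2) x sqrt(2/10).
- s = 3, e = 1.5: 2.101 x 3.674 x 0.447 = 3.45 kg
- s = 7, e = 0.5: 2.101 x 7.036 x 0.447 = 6.61 kg

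The simulated half-widths were 3.2 to 6.3 kg. The largest bias in the table is 0.91/6.3 = 14% of the half-width.

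The answer is sensitive to the dropout pattern. When leaving is concentrated wholly in one arm, two further runs gave -3.61 to -4.46 kg and -3.66 to -4.76 kg (active), and the second gave -1.38 to -2.37 kg (sham). The largest departure, 4.76 - 3 = 1.76 kg, is 1.76/6.3 = 28% of the widest half-width.

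**Step 5: limits of the mixed model.** If leaving from the active arm depends on weights not seen at scheduled visits, the mixed model is biased too, though less. Across 24 and 40 randomised it gave -3.31 to -4.59 kg, against -3.55 to -6.72 kg for complete records.

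**The case against.** **Complete-case deletion is not in the text.** That is correct. It follows from the usual form of the named method, and no other rule is given. A reader might infer that the plan decides to throw away withdrawn participants' weights. The documents do not say so; in a V1-to-end-of-study ANOVA, the early final visit could even fill the last slot. What stands is that the plan is silent on this.

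**There may be no loss after randomisation.** A reader might infer from 50 and 20 that 30 of 50 randomised people (60%) will be missing. The documents do not support this. The 50 are enrolled or consented; consent comes at V1 with the screening procedures, and assignment to arm is described under V2 to V6. Section 1 gives 10 plus 10. Some or all of the gap may precede randomisation. Scenarios with 40 randomised produce much larger biases, but they conflict with the stated allocation and I do not rely on them.

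**The endpoint's wording suits two time points.** It does, and on that reading the second point goes. Section 14 suggests more visits without settling the matter.

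**The stakes are small.** Agreed. With 24 randomised, coverage of the complete-record interval was .929 to .954.

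**Conclusion.** The point holds as a minor one. The weight analysis leaves open which visits are tested, who is included and what is estimated. The part about exclusions matters only if randomised participants miss weights. At about 24 randomised (assumed), the bias is small relative to the CI: up to 14% of the half-width in the main scenarios and 28% in the harshest pattern tried, in either direction. It would matter more only if many randomised people left. The part about the omnibus test depends on Time having more than two visits.

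Two stronger conclusions are not supported. An inflated type I error would require that no sphericity correction be applied, and the plan does not say either way. Nor does a mixed model remove all bias: it does so only as far as observed weights explain who is missing. No gain in power is claimed. Reading the study period as ending at V8 is my interpretation, since no section names a time point for weight.

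**What to change.** Replace the ANOVA sentence with:

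> Weights at V1, V6, V7 and V8 will be analysed by a likelihood-based mixed model for repeated measures (categorical visit, arm x visit after baseline, common V1 mean, REML with small-sample degrees of freedom, a simpler covariance if unstructured does not converge), including all randomised participants with a V1 weight as allocated. The main weight result is the active-minus-sham difference in change from V1 to V8 with 95% CI; V6 and V7 differences are supportive. Early end-of-study weights taken outside the V8 window are used at their actual time in a sensitivity mixed model.

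Treating V1 as an outcome keeps people who stop during V2 to V5 in the analysis set. Someone with only a V1 weight still adds little on change; the sensitivity model is where their early weight counts.

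**Cost.** Wording only: the weights are already scheduled or requested, although the vitals collected after withdrawal may not include weight. An unstructured covariance over four visits has 4 x 5/2 = 10 parameters with about 20 people, hence the fallback. The simulated mixed model was a close relative (V6 to V8 adjusted for V1 weight, six covariance parameters), which fitted in at least 1,497 of 1,500 runs per setting; the model proposed here was not itself simulated. If the team intends V1 and V8 only, saying so and reporting the difference in change with its CI settles the second point, but a rule for missing and early weights is still needed.
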